Risks that apply to both the Standard and Rapid initiation regimens include opioid withdrawal symptoms during the detoxification period, drop out from treatment prior to initiating XR-NTX and drop out from treatment once XR-NTX has been initiated. Opioid withdrawal symptoms may be unpleasant but are generally not serious, while drop out from treatment increases risk for relapse leading to overdose, disability and death. Risks of the Rapid method include the possibility of more severe precipitated withdrawal with the use of low dose oral naltrexone or after XR-NTX induction as well as side effects from standing doses of adjunctive medications. Although we expect the RP to be non-inferior to the Standard method in terms of retention and receipt of XR-NTX, there is the possibility that increased withdrawal symptoms will lead to lower rates of retention.

In a single-site randomized controlled trial conducted at an outpatient research clinic, this rapid induction method was found superior to the standard approach of buprenorphine taper followed by 7-day delay to first naltrexone dose, on proportion of patients successfully initiating XR-NTX (Sullivan *et al.*, 2017). A recent study evaluated an 8-day version of the rapid XR-NTX induction protocol (Bisaga *et al.*, 2018b) in outpatient community-based treatment programs. The overall rate of success was approximately 44% and there was no difference between participants that received buprenorphine and low-dose naltrexone in addition to adjunctive medications and those that received only adjunctive medications. The reason for not showing additional benefit of buprenorphine taper or low-dose NTX may include an extended duration of treatment which eliminates the benefits of rapid naltrexone titration (i.e., participants that received oral naltrexone may be able to receive XR-NTX earlier than on day 8). Clinical experience suggests that low dose buprenorphine at the outset is important for controlling the most severe opioid withdrawal symptoms over the first several days in patients with more severe physiological dependence and tolerance levels. The low dose naltrexone titration has a practical advantage in that it establishes with relative certainty that the patient's system is ready to tolerate naltrexone and avoids the need for naloxone challenge. In summary, this study (Bisaga *et al.*, 2018b) showed that: 1) the rapid

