Spontaneous reporting of withdrawal symptoms (including any withdrawal precipitated by the study medication) by the participant will be captured on scheduled specific structured questionnaires. Targeted safety events will not be duplicate-reported as an adverse event unless meeting the SAE definition.

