3.2.6 Targeted Safety Event

The targeted safety events (TSEs) for this study are the events listed below and recorded on the Targeted Safety Event (TSE) form:

- Fall event (related to medical/psychiatric condition such as dizziness, confusion with head injury)
- Acute change in mental status (i.e., disorientation, amnesia, cerebrovascular accident, coma)
- Acute medical complication likely exacerbated by the stress of withdrawal (i.e., hypertensive crisis, hypotensive event with medical sequelae such as fall and/or requiring urgent fluid resuscitation, severe chest pain, acute respiratory decompensation, asthma attack, diabetic ketoacidosis, severe hypoglycemia, severe electrolyte abnormalities (hyper-/hyponatremia, hyper-/hypokalemia), precipitated withdrawal)
- Acute psychiatric symptoms (i.e., psychosis, hypomania, severe agitation, violence)

Other safety events will also be captured on study specific forms (for example, COWS, SOWS, PHQ-9, Medication Injection Site Abnormality Log and Overdose Questionnaire).

TSEs and other safety events captured on study specific forms will not also be reported as an AE unless the event meets the serious adverse event (SAE) definition.

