10.1 Targeted Safety Events

Study defined targeted safety events (TSEs) are defined in Section 3.2.7. TSEs will be summarized by presenting the number and types of TSEs, relatedness to study medication, SAE classification, and number of participants experiencing TSEs by induction procedure and phase (i.e., Screening, Baseline, Induction and Post-Induction). Comparison of TSEs by induction procedure will be conducted using Fisher's exact test.

Detailed listings of TSEs by induction procedure will be provided. The listing will include Participant ID, date of IC, date of enrollment, date of TSE, TSE type and detail, severity of TSE, relatedness to study medication, SAE classification, and any additional comments collected on the form.

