	Number of TSEs				
	Type of TSE ⁷				
	Fall event ³				
	Acute change in mental status ⁴				
	Acute medical complication likely exacerbated by the stress of withdrawal ⁵				
	Acute psychiatric symptoms ⁶				
	Relationship of TSE to study medication ⁷				
	No				
	Yes				
	TSE defined as serious adverse event ⁷				
	No				
	Yes				

Table 52: Summary of Targeted Safety Events by Study Phase and Induction Procedure

Study Phase		Induction Procedure		Total (N=XX)	p-Value ⁸
		Standard (N=XX)	Rapid (N=XX)		
Screening Phase	Number of participants with at least one targeted safety event (TSE) ¹	N (X.x%)			
	Number of participants with at least one TSE of the following types ²				
	Fall event ³	N (X.x%)			
	Acute change in mental status ⁴				
	Acute medical complication likely exacerbated by the stress of withdrawal ⁵				
	Acute psychiatric symptoms ⁶				
	Number of participants with at least one TSE related to study medication ¹	N (X.x%)			
	Number of participants with at least one TSE defined as serious adverse event ¹	N (X.x%)			
	Number of TSEs	N			
	Type of TSE ⁷				
	Fall event ³	N (X.x%)			
	Acute change in mental status ⁴				
	Acute medical complication likely exacerbated by the stress of withdrawal ⁵				
	Acute psychiatric symptoms ⁶				
	Relationship of TSE to study medication ⁷				
	No	N (X.x%)			
	Yes				
	TSE defined as serious adverse event ⁷				
	No	N (X.x%)			
	Yes				

Table 52: Summary of Targeted Safety Events by Study Phase and Induction Procedure

Study Phase	Induction Procedure			
	Standard (N=XX)	Rapid (N=XX)	Total (N=XX)	p-Value⁸
Induction Phase	Number of participants with at least one targeted safety event (TSE) ¹	N (X.x%)		
	Number of participants with at least one TSE of the following types ²			
	Fall event ³	N (X.x%)		
	Acute change in mental status ⁴			
	Acute medical complication likely exacerbated by the stress of withdrawal ⁵			
	Acute psychiatric symptoms ⁶			
	Number of participants with at least one TSE related to study medication ¹	N (X.x%)		
	Number of participants with at least one TSE defined as serious adverse event ¹	N (X.x%)		
	Number of TSEs	N		
	Type of TSE ⁷			
	Fall event ³	N (X.x%)		
	Acute change in mental status ⁴			
	Acute medical complication likely exacerbated by the stress of withdrawal ⁵			
	Acute psychiatric symptoms ⁶			
	Relationship of TSE to study medication ⁷			
	No	N (X.x%)		
	Yes			
	TSE defined as serious adverse event ⁷			
	No	N (X.x%)		
	Yes			

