Table 52: Summary of Targeted Safety Events by Study Phase and Induction Procedure

Study Phase	Induction Procedure			
	Standard (N=XX)	Rapid (N=XX)	Total (N=XX)	p-Value⁸
Post-Induction Phase	Number of participants with at least one targeted safety event (TSE) ¹	N (X.x%)		
	Number of participants with at least one TSE of the following types ²			
	Fall event ³	N (X.x%)		
	Acute change in mental status ⁴			
	Acute medical complication likely exacerbated by the stress of withdrawal ⁵			
	Acute psychiatric symptoms ⁶			
	Number of participants with at least one TSE related to study medication ¹	N (X.x%)		
	Number of participants with at least one TSE defined as serious adverse event ¹	N (X.x%)		
	Number of TSEs	N		
	Type of TSE ⁷			
	Fall event ³	N (X.x%)		
	Acute change in mental status ⁴			
	Acute medical complication likely exacerbated by the stress of withdrawal ⁵			
	Acute psychiatric symptoms ⁶			
	Relationship of TSE to study medication ⁷			
	No	N (X.x%)		
	Yes			
	TSE defined as serious adverse event ⁷			
	No	N (X.x%)		
	Yes			

¹ The percentage was calculated based on the denominator of the number of enrolled participants.

² The percentage was calculated with the denominator as the number of participants with TSEs.

³ Likely related to medical/psychiatric condition such as dizziness, confusion with head injury.

⁴ Disorientation, amnesia, cerebrovascular accident, coma.

⁵ Hypertensive crisis, hypotensive event with medical sequelae such as fall and/or requiring urgent fluid resuscitation, severe chest pain, cardiac arrhythmia, acute respiratory decompensation, asthma attack, diabetic ketoacidosis, severe hypoglycemia.

⁶Acute psychiatric symptoms (i.e., psychosis, hypomania, severe agitation, violence).

⁷The percentage was calculated with the denominator as the number of TSEs.

⁸p-value is from Fisher's Exact Test.

Table 53: Summary of Study Injection Site Examinations

	Induction Procedure		
	Standard (N=XX)	Rapid (N=XX)	Total (N=XX)
Number of participants with at least one abnormal injection site ¹	N (X.x%)		
Number of abnormal injection sites	N		
Symptom experienced ²			
None	N (X.x%)		
Pain			
Tenderness			
Erythema/Redness			
Swelling			
Induration			
Abscess			
Necrosis			
Bruising			
Pruritus			
Nodule			
Hematoma			
Sterile abscess			
Cellulitis			
Warmth			
Other			
Severity ²			
Grade 1 - Mild	N (X.x%)		
Grade 2 - Moderate			
Grade 3 - Severe			

¹ Percentages were calculated based on number of enrolled participants.

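### Precipitated withdrawal, a risk the protocol names for RP, is missing from the SAP Table 52 footnote defining its category, has no by-arm count in any summary table, and may be recorded only on questionnaires

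*SAP*

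**What the plan says.** Protocol 4.1.2 names the risk for the experimental procedure: "Risks of the Rapid method include the possibility of more severe precipitated withdrawal with the use of low dose oral naltrexone".

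Protocol 12.3.13 and 17.16.3 define TSEs in four groups and direct that listed events go on the TSE form. The group for acute medical complications of withdrawal stress includes precipitated withdrawal. SAP 3.2.6 repeats the list, ending with "diabetic ketoacidosis, severe hypoglycemia, severe electrolyte abnormalities (hyper-/hyponatremia, hyper-/hypokalemia), precipitated withdrawal".

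The same two protocol sections add a sentence about questionnaires: "Spontaneous reporting of withdrawal symptoms (including any withdrawal precipitated by the study medication) by the participant will be captured on scheduled specific structured questionnaires".

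SAP 10.1 describes the output: "TSEs will be summarized by presenting the number and types of TSEs", by arm and phase, compared with Fisher's exact test. It adds a line listing: "Detailed listings of TSEs by induction procedure will be provided". In the Table 52 shell the relevant row is "Acute medical complication likely exacerbated by the stress of withdrawal". Its footnote 5 ends with "severe chest pain, cardiac arrhythmia, acute respiratory decompensation, asthma attack, diabetic ketoacidosis, severe hypoglycemia".

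**The concern.** The definition in SAP 3.2.6 and the definition printed under the results table disagree about an event on which the arms could plausibly differ. A reader of the final table would be told that the row covers cardiac arrhythmia and not precipitated withdrawal, while the governing definition says the opposite.

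Two further gaps concern the same event. Any case on the TSE form is pooled with events such as asthma attack and ketoacidosis. And the protocol does not say when an episode of precipitated withdrawal must go on the TSE form rather than being left to the questionnaires. Protocol 2.5 limits safety collection to TSEs and SAEs, so a non-serious episode recorded only on COWS or SOWS would be in no TSE or SAE output. TSEs are among the key secondary safety outcomes in SAP 8.4, and the hypothesis in SAP Table 5 is that the arms have equivalent rates.

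**Working it through.** The plan states no rate or count for this event, so there is no figure to reproduce. The check compares texts, followed by an illustration on assumed rates.

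**1. Definitions of the acute medical complication group**

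| Item | Protocol 12.3.13 | Protocol 17.16.3 | SAP 3.2.6 | SAP Table 52, footnote 5 |
|---|---|---|---|---|
| Precipitated withdrawal | yes | yes | yes | no |
| Severe electrolyte abnormalities | yes | yes | yes | no |
| Cardiac arrhythmia | no | no | no | yes |

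The first three lists agree. The footnote drops two items (in SAP 3.2.6: "severe electrolyte abnormalities (hyper-/hyponatremia, hyper-/hypokalemia), precipitated withdrawal") and adds one.

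**2. Outputs that could give a count by arm**

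- Table 52: four composite types by arm and phase, with no row for any item inside a composite. Restoring the words to footnote 5 would not create a count; a separate row would.
- TSE listings, one per arm: event description and details columns, so cases on the form can be identified and counted by hand.
- COWS, SOWS and craving tables and models: daily scores, and COWS of 12 or more. These show severity by arm but do not identify episodes that follow an antagonist dose.

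So no summary table gives the count. One listing gives it indirectly, and only for cases on the form.

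**3. Capture routes**

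Protocol 12.3.13 says that TSEs are also captured on study forms such as COWS and SOWS, which reads as recording in both places. SAP 3.2.6 makes the corresponding statement about other safety events, as if events on those forms were not TSEs. Neither document ties an episode reported on a questionnaire to the TSE form. In Protocol Table 7, COWS is not scheduled after induction. After the XR-NTX injection, SOWS at the study visits is the only scheduled withdrawal scale.

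**4. Illustration of size (assumed rates)**

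Planned RP sample: 225 (Protocol 8.0). With an assumed 3-10% having a recognised episode: 225 × 0.03 = 6.8 and 225 × 0.10 = 22.5, so about 7 to 23 participants.

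Assume further 225 per arm, 5 participants per arm with some other TSE, all precipitated withdrawal in RP, and no overlap. Two-sided Fisher's exact test, as in SAP 10.1:

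| RP cases entered on the form | RP v SP with any TSE | p |
|---|---|---|
| 0 | 5 v 5 | 1.0 |
| 7 | 12 v 5 | 0.14 |
| 15 | 20 v 5 | 0.003 |
| 23 | 28 v 5 | <0.001 |

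With 10 other TSEs per arm, 7, 15 and 23 entered cases give 17 v 10 (p = 0.23), 25 v 10 (p = 0.013) and 33 v 10 (p < 0.001). The recording route matters over most of the assumed range but not at its low end.

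**The case against.** The strongest reply is that this is a labelling error in a table shell. What enters the data is set by SAP 3.2.6 and the TSE form, and both the protocol and SAP 3.2.6 include precipitated withdrawal. A case on the form is still counted in Table 52, including in the rows for events related to study medication. No item inside a composite has its own row, so the absence of one for this event is not an anomaly. The questionnaire sentence covers what participants report spontaneously, and can stand beside the instruction to complete the TSE form. The bar on duplicate reporting concerns adverse event reports, not the TSE form.

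Much of that stands, and it rules out three stronger readings that a reader might infer:

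- That no output at all gives the count by arm. The listings do, by hand, for cases on the form.
- That the footnote is why the count is missing. The composite rows are why.
- That RP could look as safe as SP through recording alone. COWS and SOWS are compared by arm, and early induction terminations are tabulated by arm with uncomfortable withdrawal as one reason. SAP 11.0 also says that the key secondary outcomes are not confirmatory.

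What the reply does not remove is the contradiction between footnote 5 and SAP 3.2.6, or the lack of any rule linking a questionnaire report to the TSE form. The listings cannot recover cases that were never entered.

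**Conclusion.** The point holds in this form. Footnote 5 contradicts the protocol and SAP 3.2.6 on three items. No summary table reports precipitated withdrawal by arm. Cases recorded only on questionnaires would fall outside the TSE comparison and be seen only within the COWS and SOWS scores. Protocol 16.11 promises numbers and proportions for each event overall; read as each listed event, Table 52 does not deliver that either.

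The size is unknown. The 3-10% range, the 5 or 10 other TSEs per arm and the absence of SP cases are assumptions, and the Fisher illustration ignores clustering by site, as the planned test does. On those assumptions the recording route could hide or create a difference. A reader might go further and say that it could reverse the comparison; nothing in the documents shows that. Nor does Protocol 4.1.2 rank this as the main risk of RP: it is listed first, alongside side effects of adjunctive medication.

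The correction is worth making because it costs little and lets the trial report a named risk by arm.

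**What to change.** 1. Replace footnote 5 of SAP Table 52 with the SAP 3.2.6 list. In SAP 10.1, correct the cross-reference for the TSE definition from 3.2.7 to 3.2.6.
2. Add a precipitated-withdrawal row to Table 52 by arm and phase, taken from the TSE description and detail fields already in the listings.
3. Reconcile the TSE list with the questionnaire sentence in Protocol 12.3.13 and 17.16.3. The Table 55 shell already carries figures for 415 participants (190 SP, 225 RP). If those are real, enrolment is largely complete and a site instruction would change little. The report should then state how episodes were assigned to the TSE form.
4. Do not use COWS rises after naltrexone as a check between arms. The two-hour post-dose COWS belongs to the RP schedule and the titration form is collected for RP only, so cases would be found almost only there. The COWS change of 3 in the RP schedule governs dose progression and is not stated as a definition of precipitated withdrawal. At most, describe such rises within RP where assessment times were recorded.

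The cost is a corrected footnote, one extra row, a protocol clarification and a sentence in the report. The downside is that the RP TSE profile may look less favourable.

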10.7 Disposition and Referral (Phase 4)

During the last month of study, as part of standard clinical care, arrangements will be made by the clinical team for participants to either continue treatment at the same program or be referred to another program in the community for follow-up care, which should ideally include continuation of XR-NTX. The third XR-NTX injection will be administered as a part of the study in order to objectively assess the retention in treatment 8-weeks after the induction and to assure the continuation of treatment with XR-NTX during the post-study transition period. However, participants will not be followed with study assessments after third injection as at this point, they will be engaged with and followed in the community-based clinical care where they will be assessed medically following standard procedures. The disposition plan may include continuing treatment with XR-NTX or another medication in the study clinic or in a different clinic in the community. Participant may also be referred to another CTN study where long-term outcome of treatment with XR-NTX is evaluated (e.g., CTN-0100).

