16.2.3 Values of Parameters Underlying Power Simulations

Probability of Success in the SP arm: We base the assumed success probability in the SP initiation regimen on the mean success rate in the NTX arm of CTN-0051, which is 55% for sites 02011, 02017, and 02052 pooled together. These are sites that are similar to the types of sites that would be eligible for this study. These sites were chosen because they used the standard induction method (agonist taper followed by the wait). Other sites, with much higher success rates, (75%-95%) were excluded because these were already using a version of the Rapid method (no agonist taper, using only alpha-2 agonist and other non-opioid medications) or were highly experienced with XR-NTX induction.

Probability of Success in the RP arm: We assume a difference in the proportion of successes of 15% based on the results of our prior controlled study, which compared Standard and Rapid XR-NTX procedures and found a 23.4% difference (56.1% vs 32.7%) (Sullivan *et al.*, 2017). We are assuming a smaller true treatment difference (15%) between SP and RP arm, which we believe to be more realistic in the inpatient/short-term residential setting. As the proposed trial will be conducted on the inpatient unit, reducing the risk of illicit opioid use, and because sites will use regimen-driven, aggressive dosing of adjunctive medications, we believe that overall success will be 55% in the Standard Procedure arm (as in study CTN051) with the 15% difference for the Rapid Procedure arm leading to an assumed probability of success of 70% in the RP arm.

Margin of non-inferiority: To show non-inferiority of RP to SP, we assume a 10% margin of non-inferiority, which corresponds to an odds ratio of 0.67 (proportion of success in RP = 0.45, proportion of successes in SP = 0.55). To show RP is non-inferior to SP, we need to show that the lower bound of the two-sided 95% CI for the odds ratio for RP and SP is higher than 0.67.

Under the above assumptions, the null and alternative hypotheses can be stated as follows: In terms of proportions (p):

Null (inferiority of RP to SP): $p(RP) - p(SP) \leq -10\%$

Alternative (non-inferiority of RP to SP under which power was calculated): $p(RP) - p(SP)$

$> 15\%$

In terms of odds ratios (OR):

Null (inferiority of RP to SP): $OR [odds(RP)/odds(SP)] \leq 0.67$

Alternative (non-inferiority of RP to SP under which power was calculated): $OR [odds(RP)/odds(SP)] > 1.91$

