10.4 Injection Site Abnormalities

The Injection Site Abnormality (INA) form records any time an injection is given and there is an abnormal reaction observed at the injection site. Injection site abnormalities will be summarized by number of injection site abnormalities, type of abnormality, and the severity of the abnormality. A detailed listing of injection site abnormalities for injections by induction procedure will be provided. The listing will include Participant ID, date of IC, date of enrollment, date of injection, injection number, injection location, abnormality start and resolution date, symptom, severity, and SAE classification.

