Under the above assumptions, the null and alternative hypotheses can be stated as follows: In terms of proportions (p):

Null (inferiority of RP to SP): $p(RP) - p(SP) \leq -0.10$

Alternative (non-inferiority of RP to SP under which power was calculated): $p(RP) - p(SP) > 0.15$

In terms of odds ratios (OR):

Null (inferiority of RP to SP): $OR [odds(RP)/odds(SP)] \leq 0.67$

Alternative (non-inferiority of RP to SP under which power was calculated): $OR [odds(RP)/odds(SP)] > 1.91$

Intraclass Correlation Coefficient: The ICC estimate is based on a logistic regression of induction success/failure in CTN-0051 on treatment arm, with a random site effect whose variance is allowed to depend on arm. It is assumed that any extra covariates added to the model will improve

analysis accuracy, implying that current power estimates are conservative. The estimated site standard deviation in the XR-NTX arm from the regression model using data from CTN-0051 is 0.86, leading to an estimated ICC in the SP arm of 0.14 under the generalized mixed model. The ICC represents the correlation between two individuals chosen randomly without replacement from the XR-NTX arm of CTN-0051, given that they come from the same site.

In summary, the assumptions used for the power calculations for this non-inferiority optimized stepped-wedge cluster randomized trial are as follows:

- The projected number of clusters is 6 (sites), that will enroll participants across 5 periods of time, each period 14 weeks long.
- The projected total number of participants enrolled is 450, with 15 participants enrolled per cluster per time period (equal allocation to sites per time period).
- The outcome of interest is a binomial outcome (the participant received or did not receive the first XR-NTX injection).
- The probability of success in the SP arm is 0.55.
- The probability of success in the RP arm is 0.70 (i.e., an effect size of 0.15).
- The margin of non-inferiority is 10%, which corresponds to an odds ratio of 0.67 (based on proportion of success in RP = 0.45 and proportion of successes in SP = 0.55). Refer to Figure 5 for the relationship between non-inferiority margin as a difference in proportions versus non-inferiority margin as an odds ratio.
- Observations are equally correlated within cluster, regardless of time or induction method with a site standard deviation of 0.86. The corresponding ICC in the SP arm based on a logistic regression with random effects is 0.14.

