19.1.5 Treatment Exposure

Table 26: Summary of Treatment Exposure by Site					
Site	Number Enrolled	Participants with First Injection Administered While on the Unit¹	Participants with Second Injection Administered²	Participants with Third Injection Administered³	Treatment Exposure Percentage⁴
Gibson Recovery Center	N	N (X.x%)	N (X.x%)	N (X.x%)	N (X.x%)
Nexus Recovery Center					
Stony Brook Eastern Long Island Hospital					
Aspire Health Partners					
Avery Road Treatment Center					
ADAPT					
Total					

¹ Percentage was calculated as the number who had first injection administered while on the unit out of the total number enrolled.

² Percentage was calculated as the number who had second injections administered out of total number who received the first injection while on the unit.

³ Percentage was calculated as the number who had third injections administered out of total number who received the second injection.

⁴ Percentage was calculated as the number of injections administered out of the expected three injections for participants who received the first injection while on the unit.

Table 27: Summary of Treatment Exposure by Induction Procedure					
Induction Procedure	Number Enrolled	Participants with First Injection Administered While on the Unit ¹	Participants with Second Injection Administered ²	Participants with Third Injection Administered ³	Treatment Exposure Percentage ⁴
Standard	N	N (X.x%)	N (X.x%)	N (X.x%)	N (X.x%)
Rapid					
Total					

¹ Percentage was calculated as the number who had first injection administered while on the unit out of the total number enrolled.

² Percentage was calculated as the number who had second injections administered out of total number who received the first injection while on the unit.

³ Percentage was calculated as the number who had third injections administered out of total number who received the second injection.

⁴ Percentage was calculated as the number of injections administered out of the expected three injections for participants who received the first injection while on the unit.

Table 28: Summary of XR-NTX Injections in Induction Failure Participants by Site			
Site	Number Enrolled	Number of Induction Failures ¹	Induction Failures Who Had At Least One XR-NTX Injection Administered During Post-Induction Phase ²
Gibson Recovery Center	N	N (X.x%)	N (X.x%)
Nexus Recovery Center			
Stony Brook Eastern Long Island Hospital			
Aspire Health Partners			
Avery Road Treatment Center			
ADAPT			

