² Percentages were calculated based on number of abnormal injection sites.

Table 54: Summary of Non-Fatal Opioid Overdoses by Study Phase and Induction Procedure

Study Phase		Induction Procedure		Total (N=XX)
		Standard (N=XX)	Rapid (N=XX)	
Baseline (i.e., before enrollment in the study)	Number of participants with at least one overdose	N (X.x%)		
	Receive NARCAN (naloxone) at home to reverse overdose ^{1,2}			
	No	N (X.x%)		
	Yes			
	Overdose resulting in hospitalization ^{1,2}			
	No	N (X.x%)		
	Yes			
	Before the overdose, how likely was it that you would overdose ^{2,3}			
	N	N		
	Mean	X.X		
	SD	X.XX		
	Minimum	X		
	25th Percentile	X.X		
	Median	X		
	75th Percentile	X.X		
	Maximum	X		
	Before the overdose, how strongly did you want to die ^{2,3}			
	N	N		
	Mean	X.X		
	SD	X.XX		
	Minimum	X		
	25th Percentile	X.X		
	Median	X		
	75th Percentile	X.X		
	Maximum	X		
	At the time of the overdose, were you trying to kill yourself ^{2,4}			
	N	N		
	Mean	X.X		
	SD	X.XX		
	Minimum	X		

Table 54: Summary of Non-Fatal Opioid Overdoses by Study Phase and Induction Procedure

Study Phase		Induction Procedure		Total (N=XX)
		Standard (N=XX)	Rapid (N=XX)	
	25th Percentile	X.X		
	Median	X		
	75th Percentile	X.X		
	Maximum	X		
	How likely would you be to seek out certain opioids that resulted in fatal overdoses in your area ⁵			
	N	N		
	Mean	X.X		
	SD	X.XX		
	Minimum	X		
	25th Percentile	X.X		
	Median	X		
	75th Percentile	X.X		
	Maximum	X		

Table 54: Summary of Non-Fatal Opioid Overdoses by Study Phase and Induction Procedure

Study Phase		Induction Procedure		Total (N=XX)
		Standard (N=XX)	Rapid (N=XX)	
Day 1 to Day 28 Post-Induction Period	Number of participants with at least one overdose	N (X.x%)		
	Receive NARCAN (naloxone) at home to reverse overdose ^{1,2}			
	No	N (X.x%)		
	Yes			
	Overdose resulting in hospitalization ^{1,2}			
	No	N (X.x%)		
	Yes			
	Before the overdose, how likely was it that you would overdose ^{2,3}			
	N	N		
	Mean	X.X		
	SD	X.XX		
	Minimum	X		
	25th Percentile	X.X		
	Median	X		
	75th Percentile	X.X		
	Maximum	X		
	Before the overdose, how strongly did you want to die ^{2,4}			
	N	N		
	Mean	X.X		
	SD	X.XX		
	Minimum	X		
	25th Percentile	X.X		
	Median	X		
	75th Percentile	X.X		
	Maximum	X		
	At the time of the overdose, were you trying to kill yourself ^{2,5}			
	N	N		
	Mean	X.X		
	SD	X.XX		
	Minimum	X		

Table 54: Summary of Non-Fatal Opioid Overdoses by Study Phase and Induction Procedure

Study Phase		Induction Procedure		Total (N=XX)

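### SAP Table 53 divides participants with injection-site reactions by everyone enrolled, so it understates recipient risk and builds the induction difference into the comparison of procedures

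*SAP*

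**What the plan says.** SAP 10.4 bases the injection-site summary on a form that "records any time an injection is given and there is an abnormal reaction observed at the injection site". The section names no denominator. The Table 53 shell in SAP 19.1.9 does. For the row counting participants with at least one abnormal site, footnote 1 states "Percentages were calculated based on number of enrolled participants". For the symptom and severity rows, footnote 2 states "Percentages were calculated based on number of abnormal injection sites". The count of abnormal sites has no denominator. The list of outputs in SAP 18.0 assigns this table to the safety population, which SAP 3.1.4 defines as everyone who signed consent, a wider group than the enrolled.

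The planned chance of a first injection on the unit differs by procedure. SAP 12.0 says "The probability of success in the SP arm is 0.55", and Protocol 16.2.3 adds a 15-point difference, "leading to an assumed probability of success of 70% in the RP arm". Protocol 10.5.5 lets induction failures receive study-supplied XR-NTX up to week 8. SAP Table 29 counts failures who are injected during the post-induction phase.

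Elsewhere the SAP does use recipients as a base: in Table 27 the second-injection percentage is taken "out of total number who received the first injection while on the unit". On follow-up, Protocol 10.7 says "participants will not be followed with study assessments after third injection".

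**The concern.** An injection-site reaction requires an injection. Dividing by all enrolled gives the risk per recipient multiplied by the chance of ever being injected. That second factor is close to the primary outcome, which the design expects to differ between procedures. The row is laid out by procedure, so it invites a comparison of local tolerability, yet part of any difference would only reflect how many people were injected. The procedure that inducts more patients would look worse at the injection site for that reason alone.

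The level is also too low as a statement of what a recipient faces. Protocol Appendix B lists injection-site reactions as a study risk and notes that some reported cases involved surgery, so clinicians will want the recipient figure. No planned table gives a rate per recipient or per injection.

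**Working it through.** **Inputs.** Planned success p: 0.55 SP and 0.70 RP (SAP 12.0, Protocol 16.2.3). Enrolment: about 225 per procedure (Protocol 8.0). The documents give no injection-site reaction rate and no expected rate of later injection among induction failures. The recipient risk r is therefore an assumption that cancels in the ratio, and the share f of failures injected later is varied from 0 to 0.5.

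**The plan's own figures.** The two success rates reproduce the stated design. The odds ratio is (0.70/0.30)/(0.55/0.45) = 1.909 (stated 1.91). The margin is (0.45/0.55)/(0.55/0.45) = 0.669 (stated 0.67). For six sites, five steps, 15 per cell and an ICC of 0.14, an approximate calculation gives a standard error of 0.3305 for the log odds ratio. Power is then Φ[(ln 1.909 − ln 0.67)/0.3305 − 1.96] = 0.887, matching SAP Table 6. So 0.55 and 0.70 are the rates the design rests on.

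**Ratio shown when recipient risk is equal.** The probability of ever being injected is q = p + (1 − p)f. The Table 53 percentage is r × q, so the RP/SP ratio is (0.70 + 0.30f)/(0.55 + 0.45f).

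| f, equal in both arms | RP/SP ratio |
|---|---|
| 0 | 0.70/0.55 = 1.273 |
| 0.05 | 0.715/0.5725 = 1.249 |
| 0.10 | 0.730/0.595 = 1.227 |
| 0.20 | 0.760/0.640 = 1.188 |
| 0.30 | 0.790/0.685 = 1.153 |
| 0.50 | 0.850/0.775 = 1.097 |

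The difference in q is 0.15(1 − f), so at these success rates RP looks worse for every equal f below 1. With recipients as denominator the ratio is 1.00 throughout.

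**Example, r = 10%, f = 0.** The table would show 5.5% in SP (225 × 0.55 × 0.10 = 12.4 participants) and 7.0% in RP (225 × 0.70 × 0.10 = 15.75).

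**Understatement against recipient risk.** The proportional shortfall is 1 − q = (1 − p)(1 − f). At f = 0 it is 45% in SP and 30% in RP; at f = 0.30 it is 0.45 × 0.70 = 31.5% and 0.30 × 0.70 = 21%.

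**Other success rates, f = 0.** At 65% v 55%, the smallest effect in Protocol Table 11, the ratio is 1.18. If RP success were 45%, the ratio would be 0.45/0.55 = 0.82 and RP would look better.

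**Unequal later uptake.** If 20% of RP failures and no SP failures are injected later, the ratio is 0.76/0.55 = 1.38. If no RP failures but one third of SP failures are, it is 0.70/(0.55 + 0.15) = 1.00.

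**The case against.** The enrolled denominator is stated openly and is not a slip peculiar to this table: SAP Tables 50 to 52 use it for serious and targeted safety events. It answers a legitimate question, the burden per person who starts each procedure. Recipients are a subset formed after assignment and defined largely by the primary outcome, so comparing them brings its own selection. Table 27 is not a clean precedent either: its first-injection column uses all enrolled, and the recipient bases are sequential retention percentages. A reader could also approximate a recipient rate from Tables 27 and 29 and the injection-site listing.

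Much of this stands, and it argues for keeping the enrolled figure as a second, labelled row. It does not justify having no recipient figure at all. Rebuilding one from other tables is only approximate, because injections in induction failures are recorded only on the M97 form (Protocol 12.2.9). That form also holds XR-NTX from outside study supply (SAP 7.0), and Table 29 does not say that it separates the two.

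A reader might also infer that the hypothesis of equivalent safety is compromised. The documents do not support that. The hypothesis in SAP Table 5 concerns targeted safety events and SAEs, and injection-site abnormalities are not among the targeted categories in SAP 3.2.6. A reaction serious enough to be an SAE is reported as one (Protocol 12.3.13). Table 53 has no p-value.

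Nor should it be inferred that third injections are never checked and are counted as clean. Scheduled assessment ends there, but participants are asked to report reactions at once (Protocol 12.3.13), and the safety window runs to 30 days after the last visit (SAP 3.2.5). Follow-up is passive rather than absent, and the shell has no per-injection denominator in which those injections could count as clean.

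**Conclusion.** The point holds for one row of Table 53. As written, that row understates the risk to a recipient in both arms, by up to 45% in SP and 30% in RP, and carries the induction difference into the comparison. At the planned success rates and equal recipient risk, RP would appear up to about 27% higher. That maximum requires that no induction failure is injected later; with 5% to 30% equal later uptake the excess is about 25% to 15%.

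It would be easy to read 27% as the expected distortion. The documents do not support that, because success means an injection on the unit, not any injection, and later study injections are allowed. If later uptake differs by arm, the distortion could be larger, smaller or absent.

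The symptom and severity percentages do not use this denominator. The row is descriptive and untested. Neither the primary conclusion nor the hypothesis on targeted safety events and SAEs changes. The correction is still worth making before results are tabulated, because it is cheap and the recipient rate is the one clinicians need.

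**What to change.** In SAP 10.4 and Table 53:

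- Report participants with at least one abnormal site as a percentage of those who received at least one study XR-NTX injection. Take study injection as defined in SAP 7.0, and use the EOI and INN forms plus M97 for induction failures.
- Before using M97 records, confirm that the injection came from study supply. The documents do not show a field that separates study from outside supply.
- Add abnormal sites per study injection administered, using all injections. Restricting this to injections followed by a visit would drop reactions seen at the injection visit or reported spontaneously, and would condition on attendance.
- Keep the enrolled-based percentage, if wanted, as a labelled secondary row.
- Footnote that no scheduled visit follows the third injection, so later reactions rest on spontaneous report.

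The cost is a revised footnote, two added rows and a check of supply source on M97. No new data collection is needed unless that check shows supply cannot be identified. The one drawback is that recipients are selected after assignment, so the per-recipient comparison should be labelled descriptive.
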